10.2 Obligations of Investigators

The Investigator is responsible for complying with the protocol and all applicable regulations and guidelines governing clinical research. Additionally, he/she is responsible for ensuring that all participating staff members are adequately trained and competent to perform his/her assigned tasks.

All Investigators must provide the sponsor with a current *curriculum vitae*. Only Investigators and designated Sub-Investigators are permitted to sign CRFs and examination findings (e.g., laboratory results or ECGs).

The Investigator or designee is responsible for informing the patient of all available information relevant to his/her safety and obtaining signed, written consent from all participating patients. Additionally, the Investigator is responsible for monitoring patient safety and providing periodic and requested reports to the IRB/EC.

The Investigator is responsible for the accuracy and completeness of all study records including CRFs, source documents, and the Site Trial Master File. The Investigator will allow the study monitor, Sponsor, auditor, regulatory agencies, and IRB/EC full access to the study and source documents.

10.3 Institutional Review Board/Ethics Committee/Research Ethics Board (IRB/EC)

Prior to the shipment of clinical supplies or initiation of the study, the clinical trial protocol along with the informed consent form (ICF), Investigator's Brochure, and any other written information or instructions for the patient must be submitted to the IRB/EC for written approval. The Investigator will provide the Sponsor with a copy of the IRB/EC's written approval, as well as the membership list or a compliance statement

from the IRB/EC. The Investigator is responsible for notifying the IRB/EC of any Sponsor-approved amendments to the protocol or ICF, SAEs occurring in patients treated at the study site in accordance with local IRB/EC practice, and all expedited safety reports from SAEs occurring at other study sites participating in the drug development program.

10.4 Informed Consent Form

The ICF must contain all elements required by the Food and Drug Administration (FDA) under 21 Code of Federal Regulations (CFR) Part 50 and the ICH GCP guidelines (ICH E6) in addition to any other elements required by applicable national, state, provincial, and local regulations, or institutional policies.

All patients who choose to participate in the study must provide written consent after having had adequate time to consider whether they will participate in the study. The written consent must be obtained prior to any protocol-related procedures that are not part of the patient's normal medical care. The patient must be advised of his/her right to withdraw from the study at any time.

Written documentation of consent must be recorded in the patient's source documents, study records and CRF indicating the date the consent was signed. The patient should receive a signed copy of the consent form according to GCP guidelines.

10.5 Confidentiality

All information generated in this study is considered confidential, is subject to applicable privacy rules and regulations, and must not be disclosed to any person or entity not directly involved with the study unless prior written consent is gained from the Sponsor and otherwise except in accordance with applicable law or regulations. However, authorized regulatory officials, IRB/EC personnel, the Sponsor and its authorized representatives (as and to the extent authorized in the patient's ICF) are allowed access to the records.

Identification of patients in CRFs shall be by study assigned patient numbers only. If required, the patient's full name may be made known to an authorized regulatory agency or other authorized official.

10.6 Reporting of Serious Breaches of the Protocol or ICH GCP

In the event of any prohibition or restriction (i.e., clinical hold) imposed by an applicable Regulatory Authority, or if the investigator is aware of any new information which might influence the evaluation of the benefits and risks of the investigational product, the Sponsor must be informed immediately. In addition, the investigator will inform the Sponsor immediately of any serious breaches of this protocol or of ICH GCP of which the investigator becomes aware.

11 RECORDS MANAGEMENT

11.1 Source Documentation

Source documents include hospital or clinical patient charts, pertinent historical medical records, laboratory test reports, ECG tracings, pathology reports, radiographs, etc. All source documents must be legible. Data reported in CRFs and evidence of patient's informed consent must be documented in source documents.

11.2 Study Files and Records Retention

A CRF must be completed for each patient for whom informed consent for the study is obtained. The CRFs must be maintained by properly trained and delegated site representatives. The Principal Investigator has responsibility for ensuring the authenticity, accuracy, completeness and timeliness of all data collected in the CRF. CRFs must be signed by the Principal Investigator or by an authorized Sub-Investigator to attest that the information included is true.

The study site will maintain a Site Trial Master File in accordance with GCPs.

The Investigator shall retain all records for the longest of the following periods: (i) 15 years; (ii) the period of time that conforms to ICH GCP guidelines; (iii) the period of time required by applicable law or regulations, or (iv) the period of time specified in the Clinical Research Agreement.

12 QUALITY CONTROL AND QUALITY ASSURANCE

12.1 Monitoring Procedures

Sponsor appointed Site Monitor(s) must be allowed access to all study records, original source documents, and investigational products throughout the duration of the study. These personnel are responsible to assess compliance with the protocol, appropriate health authority regulations, ICH GCP guidelines, and Sponsor requirements.

The study monitor is responsible for complying with the monitoring guidelines established by the Sponsor for the study, assessing the site's needs, and liaising with the assigned Sponsor staff.

Source documents are defined as all medical records, medical notes, pathology or radiology reports, laboratory results, ECG tracings, and any additional documents that have original patient information contained within it.

If the Investigator withdraws from the study and relinquishes his/her responsibility for the maintenance and retention of records, he/she must notify the Sponsor in writing so arrangements can be made to properly store the study materials.

12.2 Auditing and Inspection Procedures

The Sponsor's Quality Assurance representatives, IRB/EC reviewers, or inspectors from regulatory agencies may perform an audit or inspection at any time during or after completion of the clinical study. All study-related documentation must be made available to the designated auditor. In addition, representatives of applicable regulatory health authorities may choose to inspect a study. A Sponsor representative will be available to assist in the preparation for such an inspection.

13 CHANGES IN STUDY CONDUCT

13.1 Protocol Amendments

Changes to the study protocol, except those intended to reduce immediate risk to study patients, may be made only by the Sponsor. A protocol change intended to eliminate an apparent immediate hazard to patients may be implemented immediately, provided the IRB/EC is notified within 5 days. Any urgent safety measures taken by the investigator to protect the study patients against any immediately life threatening hazard must be reported immediately to the Sponsor.

Any permanent change to the protocol must be handled as a protocol amendment. The change and the justification will be documented in writing by the Sponsor, as an Administrative Letter or amended protocol. Protocol amendments will be provided with a separate document describing each change and rationale. The written Administrative Letter or amendment must be submitted to the IRB/EC and the investigator must await approval before implementing the changes. The Sponsor will be responsible for submitting protocol amendments to the appropriate regulatory authorities for approval.

If in the judgment of the IRB/EC, the investigator, and/or the Sponsor, the amendment to the protocol substantially changes the study design and/or increases the potential risk to the patient and/or has an impact on the patient's involvement as a study participant, the currently approved written informed consent form will require similar modification. In such cases, informed consents (revised as appropriate to address protocol amendments) will be obtained for patients enrolled in the study before continued participation.

13.2 Protocol Deviations

Prospective permission to deviate from the eligibility criteria for this protocol will not be provided by the Sponsor. Study specified assessments should not be omitted and the study treatment regimen should not deviate from protocol specifications. Minor,

occasional adjustments in the clinic visit schedule may be necessary for logistical reasons (e.g., due to weather conditions) but must not become routine or systematically alter the study schedule. The IRB/EC should be informed of any deviations that may affect a patient's treatment or informed consent, especially those increasing potential risks, which must receive prior written approval by the IRB/EC.

14 END OF TRIAL

14.1 End of Trial in a European Union Member State

End of Trial in a Member State of the European Union is defined as the time at which it is deemed that sufficient patients have been recruited and completed the study as stated in the regulatory application (i.e., Clinical Trial Application (CTA)) and ethics application in the Member State.

14.2 End of Trial in all other Participating Countries

End of Trial in all other participating countries is defined as the time at which all patients enrolled in the study have completed the last study visit and data from those visits have been reviewed by the investigator or designee.

14.3 Premature Termination

Premature termination of this study may occur at any time because of a regulatory authority decision, change in opinion of the IRB/EC, drug safety concerns, or at the discretion of the Sponsor. In addition, the Sponsor retains the right to discontinue development of MGCD265 at any time. If termination becomes necessary, the Sponsor will inform the appropriate regulatory authorities of the termination and the reason. The Principal Investigator will inform the IRB/EC of the same. In terminating the study, the Sponsor and the Principal Investigator will assure that adequate consideration is given to the protection of the patients' interests.

15 STUDY REPORT AND PUBLICATION POLICY

The Sponsor is responsible for preparing and providing the appropriate regulatory authorities with clinical study reports according to the applicable regulatory requirements.

The publication of study results will be governed by the applicable Clinical Research Agreement between the Sponsor and the Study Site and Investigator (as applicable).

APPENDIX 1. ECOG PERFORMANCE STATUS

ECOG PERFORMANCE STATUS*	
Grade	ECOG
0	Fully active, able to carry on all pre-disease performance without restriction
1	Restricted in physically strenuous activity but ambulatory and able to carry out work of a light or sedentary nature, e.g., light house work, office work
2	Ambulatory and capable of all self care but unable to carry out any work activities. Up and about more than 50% of waking hours
3	Capable of only limited self care, confined to bed or chair more than 50% of waking hours
4	Completely disabled. Cannot carry on any self care. Totally confined to bed or chair
5	Dead

APPENDIX 2. ABBREVIATED PRESENTATION OF RECIST VERSION 1.1 GUIDELINES

A modification to RECIST 1.1 has been made to account for the possibility of temporary changes resulting from the potentially beneficial treatment response of tumor necrosis and cavitation.

Categorizing Lesions at Baseline

Measurable Lesions

- Accurately measured in at least one dimension.
- When assessed by CT or MRI, longest diameter at least 10 mm or greater (slice thickness 5-8 mm), measured in the axial plane. If the slice thickness is greater than 5 mm (including any inter-slice gap), the longest diameter must be at least twice the slice thickness.
- Malignant lymph nodes with a short axis (defined as the largest measurement perpendicular to the longest diameter of the lesion) 15 mm or greater when assessed by CT or MRI.

The shortest axis is used as the diameter for malignant lymph nodes, longest axis for all other lesions.

Non-Measurable Disease

- Lesions too small to be considered measurable (including nodes with short axis between 10 and 14.9 mm) or truly non-measurable disease such as pleural or pericardial effusions, ascites, inflammatory breast disease, leptomeningeal disease, lymphangitic involvement of skin or lung, and abdominal masses identified by physical exam that are not measurable by reproducible imaging techniques.
- Bone disease is non-measurable with the exception of soft tissue components that can be evaluated by CT or MRI and meet the definition of measurability at baseline.
- Previously irradiated lesions (or those subjected to other local treatment) are non-measurable unless they have progressed since completion of treatment.

Normal Lesions

- Non-malignant simple cysts should not be recorded either as target or non-target disease. Cystic lesions thought to represent cystic metastases can be measurable lesions, if they meet the specific definition above.
- Lymph nodes with short axis < 10 mm are considered normal and should not be followed as disease.

Tumor Assessments

All sites of disease must be assessed at baseline. Baseline assessments should be done as close as possible prior to study start. All required scans must be done within the window of time specified in the Schedule of Assessments prior to treatment. If the baseline assessment is inadequate, subsequent statuses generally should be indeterminate.

The determination of whether lesions are measurable is performed only at baseline. “Measurable” at baseline means eligible for selection as target lesions, and thus for quantitative assessment throughout the trial. Once selected as a target lesion, a lesion remains target throughout the trial.

Target Lesions

All measurable lesions up to a maximum of 2 lesions per organ, 5 lesions in total, representative of all involved organs, should be identified as target lesions at baseline. Target lesions should be selected on the basis of size (longest lesions) and suitability for accurate repeated measurements. Record the longest diameter for each lesion, except in the case of pathological lymph nodes for which the short axis should be recorded. The sum of the diameters (longest for non-nodal lesions, short axis for nodal lesions) for all target lesions at baseline will be the basis for comparison to look for partial response at later assessments.

- If 2 target lesions coalesce the longest diameter measurement of the coalesced mass is used. If a large target lesion splits, the sum of the parts is used.
- Measurements for target lesions that become small should continue to be recorded. If a target lesion becomes too small to measure, 0 mm should be recorded if the lesion is considered to have disappeared; otherwise a default value of 5 mm should be recorded.
- When nodal lesions decrease to < 10 mm (normal), the actual measurement should still be recorded.

Non-Target Lesions

All non-measurable disease is non-target. All measurable lesions not identified as target lesions are also included as non-target disease. Measurements are not required but rather qualitative evaluations of status will be recorded. Multiple non-target lesions in one organ may be recorded as a single item on the CRF (e.g., ‘multiple liver metastases’).

Objective Response Status at Each Evaluation

Disease sites must be assessed using the same technique as baseline, including consistent administration of contrast. If not, subsequent objective statuses may be indeterminate.

Target Disease

- Complete Response (CR): Complete disappearance of all target lesions with the exception of nodal disease. All target nodes must decrease to normal size (short axis < 10 mm). All target lesions must be assessed.
- Partial Response (PR): Greater than or equal to 30% decrease under baseline of the sum of diameters of all target measurable lesions. The short diameter is used in the sum for target nodes, while the longest diameter is used in the sum for all other target lesions. All target lesions must be assessed.
- Stable Disease (SD): Does not qualify for CR, PR or Progression. All target lesions must be assessed. Stable can follow PR only in the rare case that the sum increases by less than 20% from the nadir, but enough that a previously documented 30% decrease no longer holds.
- Progressive Disease (PD): 20% increase in the sum of diameters of target measurable lesions above the smallest sum observed (over baseline if no decrease in the sum is observed during therapy) with a minimum absolute increase of 5 mm.
- Indeterminate: Progression has not been documented, and
 - one or more target lesions have not been assessed,
 - or assessment methods used were inconsistent with those used at baseline and impaired assessment,
 - or one or more target lesions cannot be measured accurately (e.g., poorly visible unless due to being too small to measure),
 - or one or more target lesions were excised or irradiated and have not reappeared or increased.

Non-Target Disease

- CR: Disappearance of all non-target lesions and normalization of tumor marker levels. All lymph nodes must be ‘normal’ in size (< 10 mm short axis).
- Non-CR/Non-PD: Persistence of any non-target lesions and/or tumor marker level above the normal limits.
- PD: Unequivocal progression of pre-existing lesions. Generally the overall tumor burden must increase sufficiently to merit discontinuation of therapy. In the presence SD or PR in target disease, progression due to unequivocal increase in non-target disease should be rare.
- Indeterminate: Progression has not been determined and one or more non-target sites were not assessed or assessment methods were inconsistent with those used at baseline.

New Lesions

The appearance of any new unequivocal malignant lesion indicates PD. If a new lesion is equivocal, for example due to its small size, continued assessment will clarify the etiology. If repeat assessments confirm the lesion, then progression should be recorded on the date of the initial assessment. A lesion identified in an area not previously scanned will be considered a new lesion.

Lesion Changes That May Be Transient

Potential exists for individual tumor lesions to develop necrosis, to cavitate, have a flair response to treatment or become otherwise difficult to evaluate for a period of time as the result of beneficial study treatment impact. For example, tumor necrosis, cavitation or flair may result in increase in overall size of individual lesions or unclear tumor margins prior to recovery to smaller lesions, development of scar tissue, or complete resolution. The true tumor measurements of lesions should be recorded but the conclusion of progressive disease may be suspended until continued assessment clarifies the nature of the tumor change. If repeat assessments indicate progression of disease, then PD should be recorded on the date of the first assessment giving the impression of progression. If repeat assessments indicate that the change was a process of transition, then NE (not evaluable) should be recorded during the period of transition, and PR or CR may be recorded for subsequent evaluations. The CRF will collect information on the observations during the period of transition to support the assessment conclusions.

Supplemental Investigations

If CR determination depends on a residual lesion that decreased in size but did not disappear completely, it is recommended the residual lesion be investigated with biopsy or fine needle aspirate. If no disease is identified, objective status is CR.

Best Objective Response

Target Lesions	Non-Target Lesions	New Lesion	Point in Time Response	Best Response
CR	CR	No	CR	CR and PR require confirmation at least 4 weeks after first observation
CR	Non-CR/Non-PD	No	PR	
PR	Non-PD	No	PR	
SD	Non-PD	No	SD	SD requires an on-study assessment after at least 6weeks on treatment. Unconfirmed PR or CR are reported as SD.
PD	Any	Yes or No	PD	
Any	PD	Yes or No	PD	
Any	Any	Yes	PD	

Subjective Progression

Patients requiring discontinuation of treatment due to worsening health status attributable to advancement of the malignancy under study but without objective evidence of disease progression should not be reported as PD on tumor assessment CRFs. This should be indicated on the end of treatment CRF as off treatment due to Global Deterioration of Health Status.

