2.2 Endpoints

2.2.1 Primary Endpoints

- ORR as defined by RECIST 1.1.

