Screening/baseline tumor assessments should include CT or MRI of the chest and abdomen, pelvis, whole body bone scan, MRI of the brain and evaluation of any superficial lesions. For those sites that routinely use PET scans for assessment of bone lesions in lieu of skeletal scintigraphy, PET scans may be used on-study, with the same modality planned throughout the study for any given patient. CT or MRI of the chest, abdomen, and pelvis will be conducted at every subsequent assessment. Disease assessments subsequent to baseline assessment should also include whole body bone scans and/or MRI of the brain if metastatic disease is identified at screening/baseline by either the investigator OR the central radiology reviewer. Bone scans may be performed at one-half the frequency (every 12 weeks) of other disease assessments. All other suspected sites of disease should be evaluated at each assessment. Disease response will be assessed in accordance with RECIST 1.1 ([Eisenhauer-2009](#)). Appendix 2 provides guidance in using the response criteria and includes a modification to RECIST 1.1 to address potential temporary treatment effects such as tumor lesion cavitation. Assessments will be performed until objective disease progression is documented by the investigator, or subsequent anti-cancer therapy is begun.

Patients experiencing tumor response (Partial Response [PR] or Complete Response [CR]) should undergo confirmatory assessment at least 4 weeks after initial documentation of response. It is acceptable to perform confirmatory assessments at the next appointed evaluation per protocol. Bone scan is required as an element of the assessment of PR or CR response confirmation if bone lesions were identified at the baseline assessment. When bone scans are not protocol-specified, assessment for time point response will be based on assessment of all other lesions with imputation of Non-CR/Non-PD for bone lesions recorded as non-target lesions.

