9.4 Efficacy Endpoint Definitions and Analyses

9.4.1 Objective Response Rate

Objective disease response will be categorized in accordance with RECIST v1.1 (Appendix 2). Objective Response Rate (ORR) is defined as the percent of patients documented to have a confirmed Complete Response (CR) or Partial Response (PR), as reported by the central review laboratory. The primary analysis will be conducted approximately 12 weeks after the last patient is enrolled, allowing for observation of an early disease response and confirmation of PR or CR. ORR as reported by the investigator in the CRF will be used in secondary and supportive analyses as well as by the Internal Data Monitoring Committee for purpose of decision making using the Bayesian Predictive Probability Design.

Descriptive statistics (frequency and percentage) for ORR, CR, and PR will be presented. The exact 95% confidence interval of these response rates will be constructed. An exact test for single proportion (two-sided $\alpha=5\%$) will be performed to test $H_0: ORR \leq 20\%$ against $H_1: ORR > 20\%$. Other details will be described in the SAP.

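### The primary ORR is named as RECIST 1.1 but categorised by a modified Appendix 2 that lets progression be suspended, and the protocol does not settle whether central readers apply that rule

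*Combined protocol and SAP*

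**What the plan says.** The endpoint list in Section 2.2.1 reads "ORR as defined by RECIST 1.1". The Study Summary and Section 9.1 name the same criterion, and none of the three mentions a modification.

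Section 9.4.1 is the operative definition. It says: "Objective disease response will be categorized in accordance with RECIST v1.1 (Appendix 2"), and it counts confirmed complete or partial responses "as reported by the central review laboratory". Section 7.3 says that Appendix 2 "includes a modification to RECIST 1.1 to address potential temporary treatment effects such as tumor lesion cavitation".

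Under its subheading on transient lesion changes, Appendix 2 provides that "the conclusion of progressive disease may be suspended until continued assessment clarifies the nature of the tumor change". Two branches follow:

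- If later scans bear the progression out: "If repeat assessments indicate progression of disease, then PD should be recorded on the date of the first assessment giving the impression of progression".
- If the change is judged transitional: "then NE (not evaluable) should be recorded during the period of transition, and PR or CR may be recorded for subsequent evaluations".

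On who may suspend, Section 7.3 speaks of investigators, in the paragraph on patient management and expansion decisions. The next paragraph makes central review the basis for primary ORR, duration of response (DR) and progression-free survival (PFS), and does not repeat the permission. Appendix 2 does not restrict the rule to either assessor.

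**The concern.** The endpoint is named under one criterion and categorised under another. The difference runs one way: an assessment that would be progression can become not evaluable, after which "PR or CR may be recorded for subsequent evaluations". The protocol sets no maximum length for the suspension, no number of scans and no objective test of what counts as transitional.

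The primary test compares each arm with a fixed 20%, and there is no concurrent control read under the same rule. If central readers use the rule, any responses it adds enter the primary ORR, and the protocol specifies no ORR under unmodified RECIST 1.1 to show how many there were. Centrally read DR and PFS face the same ambiguity. The results may support an accelerated approval application (Section 3), so the criterion should be fixed before the scans are read.

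**Working it through.** **1. Which criterion governs the central read**

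| Place | Criterion or permission | Assessor |
|---|---|---|
| 2.2.1, 9.1 | RECIST 1.1 | not stated |
| 9.4.1 | RECIST 1.1, citing Appendix 2 | central review |
| 7.3, patient-management paragraph | progression may be delayed | investigators |
| 7.3, central-review paragraph | no mention of delay | central review |
| Appendix 2 | progression may be suspended | not restricted |

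The cross-reference in 9.4.1 brings the rule into the central read. Section 7.3 points the other way.

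**2. Direction**

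Compare each patient under the unmodified and modified rules.

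- Confirmed response before any apparent progression: responder under both.
- Apparent progression, borne out later: progression is dated to the first suspicious scan, so the result is the same under both.
- Apparent progression, judged transitional, then confirmed response: non-responder under the unmodified rule, responder under the modified one.
- Apparent progression, judged transitional, no confirmed response: non-responder under both.

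No case turns a responder into a non-responder. Modified ORR is therefore at least unmodified ORR in any set of patients, and the two may be equal.

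**3. Reproducing the plan's figures (Section 9.1)**

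Inputs: p0 = 20%, p1 = 40%, N = 45, success at 14 or more responses, and the listed futility boundaries from 0/10 to 13/45. An exact binomial recursion over n = 1 to 45 removes paths at or below each boundary. It gives:

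- type I error 0.0499 (stated 0.0499)
- power 0.9065 (stated 0.9065)
- probability of early termination 0.92 (stated 0.92)
- expected N 28.3 (stated 28)

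**4. The test in Section 9.4.1**

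This is an exact test at two-sided 5%. With P(X ≥ x) = Σ C(45,k) p^k (1−p)^(45−k), summed over k = x to 45, at p = 0.20:

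- P(X ≥ 14) = 0.0521, which is above 0.025; the exact lower limit for 14/45 is 18.2%.
- P(X ≥ 15) = 0.02499, just below 0.025; the exact lower limit for 15/45 is 20.0006%.

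This test therefore needs 15/45, and the 14/45 rule and the 15/45 test are shown separately below.

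**5. Sensitivity to conversions**

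The documents give no conversion frequency, so these rates are assumptions. Let the unmodified ORR be 20% (9/45 on average). Adding one or two responders per 45 gives 10/45 = 22.2% or 11/45 = 24.4%.

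| ORR as read | 14/45 with stopping | 15/45, no stopping |
|---|---|---|
| 20.0% | 0.050 | 0.025 |
| 22.2% | 0.103 | 0.058 |
| 24.4% | 0.184 | 0.114 |

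Alternatively, let a share c of non-responders be converted, so p = 0.20 + 0.80c. For c = 1%, p = 0.208 and the two chances are 0.066 and 0.035. For c = 5%, p = 0.240 and they are 0.166 and 0.101.

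At the 14/45 boundary a single conversion moves 13/45 (28.9%, no success) to 14/45 (31.1%, success).

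**The case against.** The strongest reply is that the rule is meant for investigators. Section 7.3 names only them, the transition is documented in the CRF, which is where the investigator's assessment is recorded, and the core imaging laboratory manual that would instruct central readers is not among the documents. This stands as far as it goes. A reader might infer that the central primary ORR is certainly read with suspended progression. The documents do not establish that; they show only that 9.4.1 and 7.3 conflict.

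Second, the modification is disclosed in Section 7.3 and at the head of Appendix 2. That is correct, so it is not concealed. The gap is that the endpoint and hypothesis wording omit it.

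Third, a reader might infer that the drug is judged more leniently than the treatments behind the 20%. Section 9.1 gives no response criteria for that figure, so the mismatch is possible but not shown.

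Fourth, conversion requires several steps: apparent progression, a judgement of transition, continued assessment, shrinkage of at least 30% from baseline, and confirmation at least 4 weeks later. On 6-weekly scans, progression at week 6, response at week 12 and confirmation from week 16 would miss the analysis at about 12 weeks after last enrolment for the latest patients. Conversions may therefore be few.

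Fifth, a reader might take 0.10 and 0.18 as the error rates of the primary test. They belong to the 14/45 rule and treat one stream of responses as driving both futility and success, whereas the plan uses investigator responses for stopping and central responses for the primary analysis.

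Finally, the protocol leaves detail to a SAP, and no separate SAP text is among the documents. An unmodified analysis could be planned there, but none is specified in what can be read.

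**Conclusion.** The point holds as an unresolved conflict over the criterion for the primary endpoint. As written, 9.4.1 can yield a primary ORR under a criterion other than the one named, with no unmodified result specified beside it.

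The direction follows from the rule: it cannot lower ORR and may leave it unchanged. Confirmation and backdating narrow the effect without reversing it. Backdating also means that patients whose progression is borne out gain no DR or PFS time; only changes judged transitional can lengthen those endpoints.

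The size is not known. The tabulated chances rest on an assumed one or two conversions per 45 and on a true unmodified ORR of 20%. They show that the design has almost no room for such a shift, since its stated type I error is already 0.0499 against a limit of 0.05. They do not show that the shift will occur. Reading them as bias against the null further assumes that the 20% reflects unmodified criteria.

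This should be corrected because the remedy is specific and cheap.

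**What to change.** State in Section 9.4.1 and Appendix 2 that the central read for primary ORR, DR and PFS applies RECIST 1.1 without the suspension rule. Leave the rule to investigator assessment, as Section 7.3 already has it, and report ORR under the modified rule as a sensitivity analysis. Align the core imaging laboratory manual.

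If the sponsor keeps the modification for the primary read, name the endpoint as ORR by modified RECIST 1.1 in Sections 2.2.1, 9.1 and 9.4.1 and in the Study Summary, and prespecify ORR, DR and PFS under unmodified RECIST 1.1 alongside it.

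The cost is wording and a little more analysis. All scans already go to central review and Appendix 2 already requires true measurements to be recorded, so no new imaging is needed. The downside is that a transient flare or cavitation may count as progression in the unmodified analysis; reporting both results shows how often that matters.
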